15.1 Primary Analysis

An analysis of variance (ANOVA) of the baseline log_{10} CFU/cm² values will be performed to determine whether the randomization produced treatment arms with similar baseline CFU/cm² values.

Log₁₀ reductions for the analysis of the efficacy and comparison endpoints will be calculated by subtracting the post-test material application log₁₀ recovery from the Treatment Day baseline log₁₀ recovery. Log₁₀ reductions will be calculated for all study materials for both the groin and the abdomen at the 10 minute and 6 hour sample times.

Responder rates will be calculated by converting each \log_{10} CFU/cm² reduction to a binary (yes or no) success measure. Success at 10 minutes is defined as achieving a 2 \log_{10} per cm² reduction of skin flora on the sebaceous-poor site (abdomen) and a 3 \log_{10} per cm² reduction of skin flora on the sebaceous-rich site (groin). Success at 6 hours is defined as having skin flora counts that are less than the baseline skin flora counts. Responder rates and 95% confidence intervals will be summarized for each product tested, grouped by anatomical site and each post-application time point (10 minutes and 6 hours).

The primary purpose of the study is to compare antimicrobial activity of the Investigational Product to the responder rate standards according to the FDA TFM. Investigational Product, Vehicle Control and Active Control will be compared to the efficacy standard of a 70% response rate at 10 minutes and 6 hours. It is expected that the mean responder rates will meet that standard, but since this is a Phase 2 study to inform design of future Phase 3 pivotal efficacy studies and is not designed to provide statistically powered evidence of efficacy, the confidence intervals may not lie entirely above 70%.

15.2 Secondary Analysis

The following descriptive statistics for \log_{10} CFU/cm² reductions will be computed for each product tested, grouped by anatomical site and each post application sampling time point (10 minutes and 6 hours): mean, median, standard deviation, minimum, maximum, and count.

The mean \log_{10} reductions of the Investigational Product, Active Control, and Vehicle Control will be compared to the FDA TFM standards at 10 minutes and 6 hours. The efficacy targets for the Investigational Product are mean \log_{10} reductions from baseline skin flora counts ≥ 3 for the groin and ≥ 2 for the abdomen. At the 6-hour sample time, the efficacy targets are mean \log_{10} reductions from baseline that are greater than 0 for both groin and abdomen.

Antimicrobial activity will be compared using log₁₀ reductions and responder rates between the Investigational Product, Active Control and Vehicle Control for each body area at both post treatment sampling times. Differences in log₁₀ CFU/cm² reductions between treatments and confidence intervals for will be produced by a mixed model ANOVA. Two-proportion test will be used to test differences in responder rates between treatment groups. The goal is that both the Investigational Product and Active Control demonstrate greater mean log₁₀ reductions from baseline at both 10 minutes and 6 hours and greater response rates at 10 minutes relative to the Vehicle Control.

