7.2 Secondary Analysis

Based on the mITT data / Per Protocol data, at the 10-minute sample time, the efficacy targets for the Investigational Product are mean \log_{10} reductions from baseline skin flora counts ≥ 3 for the groin and ≥ 2 for the abdomen. At the 6-hour sample time, the efficacy targets are mean \log_{10} reductions from baseline that are greater than 0 for both groin and abdomen.

Log₁₀ reductions and responder rates will be compared between study materials. The Investigational Product and Active Control should demonstrate greater mean log₁₀ reductions from baseline at both 10 minutes and 6 hours and greater response rates at 10 minutes relative to the Vehicle Control.

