7.5 Safety Analysis

The full Intent to Treat data set (all randomized subjects) will be used for the safety analysis. The principal measures of safety will be skin irritation scores and the incidence of adverse events reported during the study.

Differences between the Investigational Product, Vehicle Control, and Active Control will be evaluated on skin irritation data.

7.6 **Study Flow Chart**

Procedure	Timeline (Days)			
	14 or more	2 on more prior	0	Treatment Day
	prior to Baseline	3 or more prior to Baseline	0 Baseline	3 or more post Baseline
Informed Consent Obtained	X			
Product-Restriction Period	X	X	X	
Inclusion/Exclusion Criteria including Medical History Reviewed	X	X	X	X
Clipping Hair From Test sites		X		
Baseline Screening			X	
Test-Day Baseline Sample		= 0,		X
Product Application				X
10-Minute Post-Product Application Sample				X
6-Hour Post-Product Application Sample				X
Adverse Events		X	X	X

Note: Visual evaluations of the skin on each test area will be performed at each laboratory visit prior to treatment, and prior to 10-minute and 6-hour post-treatment microbial sampling.

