13.3 Randomization

Subjects will be randomized to treatment using the following block design:

Treatment Balance

Each subject will receive two different treatments, one on the right side of the body and one on the left. This means there are three possible combinations of treatments (assuming A and B are either Investigational Product or Active Control; C is Vehicle Control):

- A and B
- A and C
- B and C

The treatment assignments will be balanced such that the number of readings per anatomical site matches the calculated requirements. The Investigational Product and Active Control will be applied to an equal number of anatomical sites. The Vehicle Control will be compared against each active substance an equal number of times. The Vehicle Control will be applied to the number of anatomical sites necessary to generate a baseline for comparison to the active substances.

A minimum of 56 evaluable subjects will be required to achieve a total of at least 112 test sites for groin and abdominal regions. Out of the minimum 56 evaluable subjects, 40 evaluable subjects will receive treatments from both A and B, 8 evaluable subjects will receive treatments from both A and C and 8 evaluable subjects will receive treatments from both B and C to achieve 48 evaluable test sites from Investigational Product and Active Control arms (A and B) and 16 evaluable test sites from Vehicle Control arm (C) for groin and abdominal regions.

Left/Right Balance

The application will be randomized so that each treatment is used on an equal number of left and right sides of the body.

Site and Sample Time Balance

Each groin and abdomen sample site is divided into four areas and three of the areas will be sampled – one at baseline, one at 10 minutes, and one at 6 hours. The remaining area will not be used. Therefore, for any groin or abdomen site there are 24 possible sampling orders.

The number of subjects required for a completely balanced block design for all factors at once is dependent on the ratio of the number of anatomical sites used in the active treatments compared to the number of anatomical sites used in the Vehicle Control treatment but is in any case a multiple of 48 (a factor of two for left/right balance times a factor of 24 for sample order balance). The exact subject numbers and Active/Vehicle Control ratio may make it infeasible to provide a completely balanced block design, so the following priority order will be used for design:

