13.5 Baseline Screening Procedures

Baseline-screening samples will be taken on the day following the-14 day pre-test period. Subjects will not shower at least 72 hours prior to being sampled. Subjects will don a disposable undergarment prior to baseline screening procedures and will be examined physically to ensure that there is no evidence of injury, dermatosis, folliculitis, or dermatitis present at the sampling sites (Section 14.2). A subject will be dismissed from the study if skin irritation score of 1 is observed on the test sites. If the subject continues to meet the qualification criteria, they will be sampled using the Cylinder Sampling (Scrub Cup) Technique (Section 13.7) at the center of the sampling areas on the skin of the inguina and abdomen (Appendix 2). There will be a minimum of 72 hours between the time the screening period ends and the experimental period begins. Based upon adequate screening microbial counts, subjects will be eligible to continue into the treatment phase of the study. Subjects may qualify on one or two anatomical site(s) and be admitted into testing for those anatomical site(s) only, although if more subjects qualify for treatment than can be treated in a given time period, preferential admittance into the treatment phase will be given to subjects qualifying in both the abdominal and inguinal test areas.

Baseline criteria for qualification for the test period are $\geq 3.11 \log_{10} \text{ CFU/cm}^2$ from the skin of the abdomen, and/or $\geq 5.50 \log_{10} \text{ CFU/cm}^2$ from the skin of the groin.

There will be a minimum of 72 hours between baseline screening procedures and treatment day procedures. Based upon achieving adequate baseline screening microbial counts, subjects will be eligible to continue to treatment day procedures.

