14.0 ASSESSMENT OF SAFETY

14.1 **Safety Assessments**

The subject's safety will be monitored by evaluations of reactions observed on the skin of the test sites and any adverse reactions. Adverse reactions will be documented per BSLI Standard Operating Procedure, reported as an Adverse Event, and followed to resolution.

14.2 **Evaluation of Test Sites**

Prior to product application and before any subsequent samples, test site erythema, edema, rash, and dryness will be rated on a 4-step scale, the Skin Irritation Scoring System (Draize). If a subject receives a score of 1 for erythema, edema, rash, and/or dryness prior to Screening Baseline Day or product application on Treatment Day, they will be dismissed from testing. If a subject receives a score of 3 for erythema, edema, rash, and/or dryness at any point in the study, they will be dismissed from testing and reported as an adverse event. (Note: Skin irritation scores of 1 or 2 are expected after sampling and product application procedures and are not grounds for dismissal and will not be considered adverse events.)

SKIN IRRITATION SCORING SYSTEM (Draize)

	0	No reaction
E 41	1	Mild and/or transient redness limited to sensitive area
Erythema	2	Moderate redness persisting over much of the product-exposed area
	3 *	Severe redness extending over most or all of the product-exposed area
	0	No reaction
17.1	1	Mild and/or transient swelling limited to sensitive area
Edema	2	Moderate swelling persisting over much of the product-exposed area
	3 *	Severe swelling extending over most or all of the product-exposed
0		No reaction
Rash	1	Mild and/or transient rash limited to sensitive area
Rasn	2	Moderate rash persisting over much of the product-exposed area
	3 *	Severe rash extending over most or all of the product-exposed area
0 No reaction 1 Mild and/or tr		No reaction
		Mild and/or transient dryness limited to sensitive area
Dryness	2	Moderate dryness persisting over much of the product-exposed area
	3 *	Severe dryness extending over most of all of the product-exposed area

^{*} A score of 3 in one or more of the conditions evaluated represents significant irritation and qualifies as an Adverse Event.

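### Minor: responder rates for the investigational product and active control are compared as independent groups although 40 of 48 sites per product share a subject, and the irritation test has no stated unit

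*Combined protocol and SAP*

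**What the plan says.** **Design.** Section 13.3: "Each subject will receive two different treatments, one on the right side of the body and one on the left". The same section sets out the pairing for a minimum of 56 people. For the largest group it states: "40 evaluable subjects will receive treatments from both A and B". The other 16 split evenly, half getting A with C and half getting B with C. A and B are the investigational product (IP) and the active control (AC); C is the vehicle.

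**Responders.** Section 7.2 plans that "responder rates will be compared between study materials". Section 15.2 applies this to all three products, by body area and sampling time, and names the method: "Two-proportion test will be used to test differences in responder rates between treatment groups". For log reductions from the same sites it names a mixed model ANOVA, which can carry a subject effect.

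**Irritation.** Section 7.5: "Differences between the Investigational Product, Vehicle Control, and Active Control will be evaluated on skin irritation data". Section 15.4 reduces the four skin categories to any score above zero, counts that as a signal for the product, and names Fisher's exact test. It does not say whether the unit is a subject-product combination, a test site or a single rating. Nor does it say whether products are tested pairwise or all three together. Under Section 14.2 each site is rated repeatedly, and "Skin irritation scores of 1 or 2 are expected after sampling and product application procedures". Section 13.5 adds: "Subjects may qualify on one or two anatomical site(s) and be admitted into testing for those anatomical site(s) only". The number of sites can therefore differ between subjects.

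Section 15.0 leaves further detail to a separate SAP, which is not in the supplied text.

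**The concern.** Both named tests for yes/no outcomes assume that the two products were tested on different people. For IP versus AC that is untrue of most sites. When two sites on one person tend to agree, the difference between them is less variable than an independent-groups formula assumes. The planned test then reports too large a standard error and does not use the precision that the split-body design was set up to give.

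For irritation the missing unit adds a second problem. With one result per subject and product, only the pairing matters and the error is conservative. If several sites or repeated ratings on one person are counted as separate units, clustering within a product works the other way and can raise the false-positive rate above 5%.

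The stakes are a secondary contrast and a safety contrast in a Phase 2 study meant to inform Phase 3 design.

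**Working it through.** **1. The plan's own figures.** IP 40 + 8 = 48 sites; AC 40 + 8 = 48; vehicle 8 + 8 = 16. Subjects 40 + 8 + 8 = 56; sites 2 × 56 = 112 per region. All agree with Section 13.3. The paired share of IP sites, and of AC sites, is 40/48 = 83%.

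**2. Responders, IP versus AC.** Let p be a common responder rate and rho the left/right correlation of the yes/no outcome. The documents give no rho; 0 to 0.5 is assumed. They also give no significance level for this test; two-sided 5% is assumed, in line with the 95% intervals in 15.1.

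- Variance the test assumes: 2p(1−p)/48.
- True variance with 40 pairs: 2p(1−p)/48 × [1 − (40/48)·rho].
- Overstatement of the standard error: 1/√[1 − (40/48)·rho] − 1.
- True level: 2Φ(−1.96/√[1 − (40/48)·rho]).

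| rho | variance factor | SE overstated | true level of nominal 5% |
|---|---|---|---|
| 0 | 1.000 | 0% | 5.0% |
| 0.1 | 0.917 | 4% | 4.1% |
| 0.2 | 0.833 | 10% | 3.2% |
| 0.3 | 0.750 | 15% | 2.4% |
| 0.5 | 0.583 | 31% | 1.0% |

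If site-level exclusions leave 32 or 24 complete pairs out of 48 sites, the overstatement at rho 0.3 is 12% (factor 1 − (32/48) × 0.3 = 0.80) or 8% (factor 0.85).

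**3. Power.** Simulation of the 40/8/8 design at assumed rates of 85% and 65%:

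| rho | two-proportion test | subject-clustered test |
|---|---|---|
| 0 | about 64% | 62–63% |
| about 0.1 | about 64% | 65–67% |
| 0.25–0.28 | 64–66% | 72–74% |

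With 20% of sites lost (32 pairs, 48 sites per product), the figures are 63 vs 62%, 64 vs 66% and 64 vs 70% at rho 0, 0.11 and 0.28. The clustered test, with a small-sample correction, held its level at 4.5–5.2% for true rates of 10–90%, and at 3.1–4.5% for a rate of 95%.

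**4. Responders, active versus vehicle.** Eight subjects are shared between 48 and 16 sites. The factor is 1 − [2 × 8·rho/(48 × 16)]/(1/48 + 1/16) = 1 − 0.25·rho. The standard error is overstated by 1% at rho 0.1 and 7% at rho 0.5. At rho 0.3 the level is 4.2%.

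**5. Irritation, IP versus AC.** With k results per subject and product, correlation rw within a product and rb across products in one subject, the variance factor is 1 + (k−1)·rw − (40/48)·k·rb. The implied levels below are before Fisher's own conservatism:

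| unit | k | rw = rb = 0.3 | rw = 0.3, rb = 0.1 |
|---|---|---|---|
| subject and product | 1 | 0.75 → 2.4% | 0.917 → 4.1% |
| site (two regions) | 2 | 0.80 → 2.8% | 1.133 → 6.6% |
| site and time (two regions, two times) | 4 | 0.90 → 3.9% | 1.567 → 11.7% |

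Simulated Fisher levels, with assumed site-level correlations of 0 to 0.37 and per-rating rates of 15 to 50%:

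| unit | IP vs AC | IP vs vehicle |
|---|---|---|
| subject and product | 0.6–3.4% | 1.7–4.4% |
| site | 1.6–6.9% | 3.8–7.9% |
| site and time | 3.7–14.9% | 5.9–16.9% |

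These runs use 48/48/16, the evaluable minimum. The safety set is all randomized subjects, so the actual denominators will differ.

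**The case against.** **Nothing decided in the trial depends on IP versus AC.** This stands. The goal in 15.2 is for each active to exceed vehicle. IP versus AC has no target, margin or rule, Section 7.4 disclaims powering, and the mixed model on log reductions recovers part of the within-subject information. The 70% comparison is also untouched, since each product contributes at most one site per subject per region to its own rate. The point is therefore minor.

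**The test is only conservative.** This stands too. A reader might infer that the planned test loses power as the two sides become more alike. It does not: its power stays at about 64 to 66%. What it misses is the gain available from the pairing.

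**Section 15.4 can be read sensibly.** One result per subject and substance is the most natural reading, and Fisher's test is then conservative. Counting every rating separately is the least natural, so the highest levels above show what the wording permits, not what to expect.

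**The 15.4 follow-up.** A reader might infer that a significant IP-AC irritation result starts it. The text ties it to differences between the two actives and vehicle, so only the choice of unit bears on that trigger. The consequence is a further descriptive look.

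**Irritation power.** A reader might credit pairing with the whole gain from replacing Fisher's test. At assumed rates of 30% and 10% and rho 0.23, power is 62% for Fisher, 74% for a pooled test that ignores pairing, and 79% for a clustered test. Of the 17 points, 12 come from leaving Fisher's test and 5 from the pairing.

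**The separate SAP may settle both points.** It may. The protocol nevertheless names specific tests, and the two should agree.

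**Conclusion.** The point holds and is minor. The responder test in 15.2 has the wrong standard error for IP versus AC under any positive left/right correlation. The size depends on a correlation that the documents do not give: nothing at 0, a 15% overstatement and a 2.4% level at 0.3, and 31% and 1.0% at 0.5, with all 40 pairs complete. The direction is conservative, so the documents do not support any suggestion of false claims of a responder difference.

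For irritation, 15.4 shares the independence problem for IP versus AC, but the main gap is the undefined unit. On the natural reading the test is conservative. On a site or rating basis its level could exceed 5%, depending on correlations that are also assumed here.

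The primary comparison is unaffected and comparisons with vehicle are little affected by the pairing.

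**What to change.** **Section 15.2, IP versus AC, by body area and time.** Report the difference in responder proportions over all included sites, with a 95% interval from a variance that accounts for subject. One suitable choice is an identity-link GEE with subject as cluster and a small-sample correction; an equivalent method for partly paired data would serve as well. Keep sites whose partner is missing or excluded. McNemar's test on the 40 pairs alone drops the other 8 + 8 sites and is weaker at low correlation: at assumed rates of 90% and 70% with rho 0, its power is 60% against 72% for the two-proportion test. If there is no variation in the outcome, report counts only.

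**Section 15.4.** Define one yes/no result per subject and product: any post-application score above zero, in any category, on any site treated with that product. State whether comparisons are pairwise. Account for subject in IP versus AC, with the same fallback when there is no variation.

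**Vehicle comparisons.** Keep the named tests, with the same irritation unit, and note that they ignore the 8 subjects shared with each active.

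**Cost.** Three or four sentences in 15.2 and 15.4 or in the separate SAP, and a few lines of code; no new data or subjects. The analysis is slightly more complex, with no gain, or a loss of about 1 to 2 power points, when the correlation is near zero.

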15.3 Exploratory Analysis

Product Expression Volumes:

The weight (grams) of drug product solutions applied to a treatment area will be estimated as:

Product weight prior to treatment (g) – product weight post-treatment (g)

[figure not shown]
The following descriptive statistics for expression volumes will be computed for each product tested at each anatomical site: mean, median, standard deviation, minimum, maximum, and count. An analysis of variance (ANOVA) of the applied volumes will be performed to determine whether the treatment arms had similar volumes applied. If a significant difference is found, differences between groups will be examined by appropriate follow up tests. Analysis for product expression volumes will be based on the mITT data / Per Protocol data.

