7.3 Exploratory Analysis

Based on the mITT data / Per Protocol data, the weight (grams) of drug product solution applied to a treatment area will be compared between study materials for each body area from the product weight measured pre and post application.

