13.6 Treatment Day Procedures

Prior to sampling, the subjects will be questioned regarding adherence to the qualification criteria.

Subjects will don a disposable undergarment and be examined physically to ensure no evidence of injury, dermatosis, or dermatitis is present in the test areas. One sterile surgical marker will be used per subject. The marker will be used to demarcate a 5" × 5" areas of skin on the right and left sides of the abdomen, adjacent to the navel that appear to be similar in condition. The marker will again be used to demarcate 2" x 5" areas of skin in the inguinal areas that appear to be similar in condition. During treatment day procedures, subjects will wear disposable gloves to guard against contamination of the test sites.

Subjects will be sampled for treatment day baseline microbial populations on randomly assigned sites of the abdominal and inguinal areas on both sides (Appendix 2). The Cylinder Sampling (Cup Scrub) Technique (Section 13.7) will be used for baseline and post-treatment samples.

All product treatments for a subject will be completed on a single day (Treatment Day). The test materials will be applied to the test sites in accordance with the randomization schedule using repeated back-and-forth strokes for 3 minutes on both abdominal and inguinal test sites with a dry time of 1 minute. Detailed instructions on product application are presented in Appendix 1. All test materials will be weighed before and after application and the weights will be recorded. All subjects will have samples collected 10 minutes \pm 30 seconds and 6 hours \pm 30 minutes post product application on both abdomen and inguinal sites. All sampling times will be calculated from the completion of the dry time of each product following application.

Following collection of the last 6 hours \pm 30 minutes post-product application sample of a test site, the remaining test material will be wiped/cleansed from the test site with a mild soap and/or tap water; test sites will be dried with paper towel.

Cylinder Sampling (Scrub Cup) Technique 13.7

Abdomen and Inguinal Samples

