13.10 Data Handling

The estimated log₁₀ number of viable microorganisms per cm² recovered from each sample site will be designated the "R-value."

To convert the volumetric measure of the sample into the number of colony-forming units per square centimeter (cm²), the following formula will be employed:

$$R = \log_{10} \left[\frac{F\left(\frac{\sum c_i}{n}\right) 10^{-D}}{A} \right]$$

where:

R = the average colony-forming unit count in log_{10} scale per cm² of sampling surface

F = total number of mL of stripping fluid added to the sampling cylinder; in thisstudy, F = 6 mL for all samples

 $\frac{\sum c_i}{n}$ = average of the duplicate colony counts used for each sample collected

D =dilution factor of the plate counts

A = inside area of the cylinder in cm²; in this study, $A = 3.46 \text{ cm}^2$ (2.1 cm i.d.)

NOTE: The reason that a log₁₀ transformation will be performed on the collected data is to obtain a linear scale. A linear scale, more appropriately a log₁₀ linear scale, is a basic requirement of the statistical models used in this study.

If colonies on one of the plates are uncountable, the count from the remaining plate will be used. In order to avoid potential calculation problems due to taking the logarithm of zero, counts of zero will be considered 1 for further calculations.

Data collected from subjects with low test-day baseline counts on an anatomical test site ($< 3.11 \log_{10} \text{CFU/cm}^2$ from the skin of the abdomen, or $< 5.50 \log_{10} \text{CFU/cm}^2$ on the skin on the inguen) will not be used in the mITT Efficacy Analyses (Section 15.0).

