15.0 STATISTICAL METHODS

Data processing and statistical analysis for this study will be conducted by the BD statistical group based on the final monitored data provided by the Testing Facility to the BD statistical group.

Details of the statistical analysis will be provided in a separate statistical analysis plan.

Data sets analyzed

The full intent to treat (ITT) data set (all randomized subjects) will be used for the safety analysis.

A modified Intent to Treat (mITT) data set will be used for efficacy analyses. Inclusion for the mITT data set is evaluated for each body area (left and right for the groin and abdomen). For each body area, if the treatment day baseline bacterial count requirements are in the range of 3.11 to 5.50 log₁₀/cm², inclusive, on the abdomen and 5.50 to 7.50 log₁₀/cm², inclusive, on the groin, then the data from that body area are included in the mITT data set. Efficacy analyses will also be conducted on the Per Protocol data set as supportive analyses when Per Protocol data are different from mITT data.

- For responder rate, missing data will be treated as non-responders in the mITT data, while in the Per Protocol data, missing data will not be imputed and will be excluded from the responder rate Per Protocol analysis.
- For log reduction, missing data will not be imputed for either mITT data or Per Protocol data and will be excluded from log reduction analysis.

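### The product-weight comparison drops valid weights because of a bacterial count and names an ANOVA with no subject term, at some cost in precision and sensitivity

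*Combined protocol and SAP*

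**What the plan says.** Section 13.6 requires that "All test materials will be weighed before and after application and the weights will be recorded", with no condition on bacterial count. Section 7.3 says that "the weight (grams) of drug product solution applied to a treatment area will be compared between study materials for each body area", and places this comparison on the mITT / Per Protocol data. Section 15.3 repeats the restriction: "Analysis for product expression volumes will be based on the mITT data / Per Protocol data".

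Sections 7.1 and 15.0 define the mITT set for the efficacy analyses. They decide inclusion separately for each side of the abdomen and groin, by whether the Treatment Day baseline count lies in 3.11–5.50 (abdomen) or 5.50–7.50 (groin) log10/cm².

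For the test, Section 15.3 plans an ANOVA "to determine whether the treatment arms had similar volumes applied", with follow-up tests only if it is significant. It lists descriptive statistics but no confidence interval, and it names no model terms. Section 15.2 specifies a mixed model ANOVA for the log10 reductions. Section 13.3 sets the pairing: "Each subject will receive two different treatments, one on the right side of the body and one on the left". Section 15.0 leaves further detail to a separate statistical analysis plan, whose text is not in the document reviewed.

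**The concern.** The count range decides whether a log reduction at a site can be judged fairly. It has no bearing on whether the change in a cloth's weight was measured properly. Baseline sampling and treatment fall on the same day (Section 13.6), while plates incubate for about 72 hours (Section 13.8). An out-of-range count is therefore known only after the site has been treated and weighed, and a sound measurement is then discarded.

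The second issue is pairing. Two products applied to the same subject may share influences such as skin condition or the person applying them. If so, a model without a subject term leaves between-subject variation in the error, and the comparison loses sensitivity.

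This is the only planned comparison of how much solution each product delivers, in a study meant to inform Phase 3 design (Section 7.4). Because follow-up tests depend on a significant overall result, a missed difference would end the inquiry there.

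**Working it through.** **The plan's own figures.** Section 13.3 allocates 40 subjects to A+B, 8 to A+C and 8 to B+C, where A and B are the Investigational Product and Active Control and C is the Vehicle Control. Sites per region:

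- A: 40 + 8 = 48
- B: 40 + 8 = 48
- C: 8 + 8 = 16
- Total: 112 = 2 × 56 subjects, as stated.

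The documents give no figure for the weight analysis itself.

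**Part 1: sites lost to the count rule.** The share f of treated sites outside the range is not in the documents, so 5–30% is an assumption. If sites are lost evenly across products, the standard error (SE) is multiplied by 1/√(1 − f):

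- f = 5%: 1/√0.95 = 1.026
- f = 10%: 1/√0.90 = 1.054
- f = 20%: 1/√0.80 = 1.118
- f = 30%: 1/√0.70 = 1.195

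The SE is thus about 3% to 20% larger.

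**Part 2: no subject term.** Take the full 40/8/8 layout, a site SD of 1, and a correlation ρ between the two sides of a subject. The documents do not give ρ, so the values below are assumed. For A minus B:

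- One-way ANOVA SE = √(1/48 + 1/48) = 0.204, whatever ρ is. The two sides always carry different products, so the expected residual mean square stays at 1.
- True SE of that same difference in means = √[(2/48)(1 − ρ × 40/48)].
- Mixed-model SE = √[2(1 − ρ²)/(48 + 40ρ)], taking the variance components as known.

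| ρ | One-way ANOVA SE | True SE of same difference | Mixed-model SE | One-way / mixed |
|---|---|---|---|---|
| 0 | 0.204 | 0.204 | 0.204 | 1.00 |
| 0.3 | 0.204 | 0.177 | 0.174 | 1.17 |
| 0.5 | 0.204 | 0.156 | 0.149 | 1.37 |

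At ρ = 0.3 the mixed-model variance is 2 × 0.91/60 = 0.0303. At ρ = 0.5 it is 2 × 0.75/68 = 0.0221.

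For A minus C at ρ = 0.5, the one-way SE is 0.289 and the mixed-model SE 0.237, a ratio of 1.22.

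**Direction of the error.** The overall one-way F test was simulated in this layout at a nominal 5% (40,000 runs per value). Its type I error was 5.1% at ρ = 0, 3.8% at 0.2, 2.2% at 0.5 and 1.1% at 0.8. With positive correlation the test rejects too rarely.

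The results of the two parts should not be multiplied together. Part 2 assumes all pairs are intact, and exclusion by side breaks pairs. If 20% of sites dropped out independently, 0.8 × 0.8 = 64% of pairs would remain.

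**The case against.** **The restriction may be deliberate.** If the weights are meant to help interpret efficacy differences, it is coherent to use the same sites as the efficacy analysis. This stands as a reason to keep the mITT version as a companion. It is not a reason to leave the other weights unanalysed.

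**Bias.** A reader might infer that the exclusion distorts the comparison of products. The documents do not support that. The count comes from a sample taken before treatment, sides are randomised, and those counting plates are blinded to the randomisation (Section 13.9). The loss is one of precision.

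**Independence.** A reader might also infer that the plan treats the two sides as independent. Section 15.3 does not say so. It names an ANOVA without terms, and a subject term could still appear in the separate analysis plan. The contrast with Section 15.2 makes the plain reading a fair inference, but no more.

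**Wrong error bars or false positives.** No interval for weights is planned, so none can be wrong. Positive correlation makes the test conservative, and at zero correlation there is no error. Nothing in the documents shows that solution released from two different cloths correlates within a subject.

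**Size.** The familiar pairing factor 1/√(1 − ρ), which gives 1.20 at 0.3 and 1.41 at 0.5, describes only the 40 A+B subjects. The full layout gives 1.17 and 1.37.

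**Conclusion.** The analysis-set point holds on the text: Sections 7.3 and 15.3 exclude validly recorded weights by a rule designed for efficacy. The SE cost is about 3–20% under the assumed 5–30% of sites out of range.

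The pairing point holds as a gap in specification. If no subject term is used, the SE for A minus B is about 17–37% larger than a mixed model's at correlations of 0.3–0.5, and a real difference in delivered weight could be missed. Both sizes rest on quantities that the documents do not report.

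The endpoint is exploratory in a study with no power calculation (Section 7.4), so the effect on the trial's main conclusions is small. This is a cheap improvement, not a threat to validity.

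**What to change.** In Sections 7.3 and 15.3, and in the separate analysis plan:

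- Analyse weights from all treated sites with a recorded weight, separately for abdomen and groin.
- Use a mixed model with treatment as a fixed effect and subject as a random effect, in line with Section 15.2.
- Report the differences between products with 95% confidence intervals.
- Keep the mITT version as a companion analysis if alignment with the efficacy set is wanted.

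The cost is a small wording change. Since the text is in the protocol, Section 16.2 would send it to the IRB as a written amendment. No new data, visits or subjects are needed, because the weights are already to be recorded.
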